## 5 Study Design

### 5.1 Overview of Study Design

This is a multi-center, open-label, 12-month clinical trial of ACTIMMUNE treatment of patients with intermediate osteopetrosis. Study design is summarized in Figure 1. Routine clinical safety and efficacy data (see Table 1) will be obtained at baseline, weeks 4 and 6, and months 3, 6, 9, and 12

following the initiation of therapy. Additional outcomes (see Table 1) will be obtained at baseline, 3, 6 and 12 months.

\*Includes medical history, ECHO, and EKG.

Fig. 1. Study Design Schematic

## 5.2 Anticipated Duration of the Clinical Investigation

Each subject will be enrolled in the study for 12 months. It is expected that 15 patients will be screened over 18 months to enroll 10 participants, with the final subject completing study participation 2.5 years after study initiation. The final study report will be completed approximately 3 years after study initiation. If the study is terminated prior to completion, a closeout report will be filed with the Institutional Review Board (IRB) within 3 months of study termination.

## 5.3 Evaluations and study timeline

Table 1. Evaluations and study timeline

	Screening a	Baseline	# of months from 1 st IFN- $\gamma$ 1b treatment ( $\pm$ 1 week)		
			3	6	12
General					
• Medical history	X	X	X	X	X
• Physical exam		X	X	X	X
• Genotype b		X			
• Anthropometric measurements	X	X f	X	X	X
• RNA and DNA assays		X	X	X	X
Safety Measuresc					
• Basic metabolic panel (BMP)	X	X	X	X	X
• Liver function tests (LFT)	X	X	X	X	X
• Urine pregnancy test (UPT) e	X	X	X	X	X
• Urinalysis (UA)	X	X	X	X	X
• ECHO with interpretation	X				
• EKG with interpretation	X				

• Anti-drug antibodies (ADA) g		X	X	X	X
Bone Biomarker Testingd					
• Formation Testing (bone specific alkaline phosphatase [BAP], type 1 procollagen [P1NP])	-	X	X	X	X
• Resorption testing (C-telopeptide [CTX], Tartrate resistant acid phosphatase type5b [TRAP5b])	-	X	X	X	X
• RANKL, OPG, CK-BB	-	X	X	X	X
Endocrine Assessment					
• Total 25-OH Vitamin D (25OHD) h	-	X	X	X	X
• Serum ionized calcium	-	X	X	X	X
• Urine calcium: creatinine	-	X	X	X	X
• Intact parathyroid hormone (iPTH)	-	X	X	X	X
Inflammatory/Immunology					
• CBC with differential and platelets	-	X f	X	X	X
• Erythrocyte sedimentation rate (ESR)	-	X f	X	X	X
• Immunologic phenotyping (CD3, 4, 8, 14, 15, 16, 19, 34, 56)	-	X	X	X	X
Neuropsychological testing					
• Pain assessment	-	X	X	X	X
• Quality of life survey	-	X	X	X	X
Orthopedic assessment					
• Dual energy X-ray absorptiometry (DXA) lumbar spine, total body, total hip and femoral neck (adults $\geq 18$ yrs only)	-	X	-	-	X
• Peripheral Quantitative CT (pQCT) left tibia	-	X	-	X	X
In vitro osteoclast function assays – [name] Lab					
• Gene expression – osteoclast marker genes	-	X	X	X	X
• Osteoclast activity – ability to release calcium phos from coated plate	-	X	X	X	X
Infectious outcomes					
• Number of hospitalizations in prior 3 months	-	X f	X	X	X
• Number of days treated with antibiotics in last 3 months	-	X f	X	X	X
• Type of infectious organism	-	X f	X	X	X
RANKL=Receptor activator of nuclear factor kappa-B ligand; OPG=osteoprotegerin; CK-BB=creatinine kinase isoenzyme BB.					
a Screening visit evaluations will count for baseline evaluations where applicable. Screening visit will be within 3 months of baseline visit					
b Genetic testing for CLCN7, CAII, TCIRG1, OSTM1, and RANKL mutations will be done at the University of Minnesota if not already performed clinically					
c Safety labs will also be obtained at weeks 4 and $6 \pm 2$ days, and month $9 \pm 1$ week; subjects will be contacted on a weekly basis either by email or telephone to monitor safety during the initial 4 week dose escalation period.					
d Sample collection will be postponed if needed to ensure collection is more than 2 weeks since last fever ( $>100.4^{\circ}\text{F}$ [ $38^{\circ}\text{C}$ ] axillary) or fracture.					
e Post-menarchal females.					
f Height (for subjects $<18$ years), CBC, and ESR will be obtain from the patient's medical record when available and number of hospitalizations and infectious data from the patient's medical record or if not available then the patient's recollection at the baseline visit.					
g ADA testing will also be performed at weeks 3 and $6 \pm 2$ days after the first dose, and 2-3 weeks after last dose, and then every 4-6 weeks until values return to baseline.					
h 25OHD level will be checked at 6 weeks as well.					

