### 4.2 Secondary Hypotheses

The secondary hypotheses are:

1. Compared to baseline, treatment with IFN- $\gamma$ 1b will result in:
  - a. Decreased tibial volumetric bone mineral density (**vBMD**) and estimated bone strength measured by peripheral quantitative computed tomography (**pQCT**);
  - b. Decreased total body and lumbar spine areal BMD (**aBMD**) by dual-energy x-ray absorptiometry (**DXA**);
  - c. Increased levels of markers of bone remodeling (see Table 1);
  - d. Increased osteoclast activity by *in vitro* testing;
  - e. Increased white blood cell (**WBC**) and platelet counts in patients that have lower than expected blood counts at baseline.
  - f. Increased height standard deviation score (**SDS**) for participants <18 years with open growth plates;
  - g. Decreased inflammation measured by erythrocyte sedimentation rate (**ESR**);

[figure not shown]
- h. Decreased pain score (based on prior 4 weeks);
  - i. Increased physical function score (based on prior 4 weeks); and
2. Compared to the 12 months prior to study entry (based on medical record review or subject recollection), treatment with IFN- $\gamma$ 1b over 12 months will result in:
  - a. Decreased number of hospitalizations for infection;
  - b. Decreased number of days treated with antibiotics;
  - c. Beneficial change in WBC and platelet counts in patients who have lower than expected blood counts at baseline;
  - d. Beneficial change in ESR;
  - e. Increased height SDS for participants  $<18$  years with open growth plates; and
3. Patients will not develop neutralizing antibodies.

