## **6.2 Laboratory Testing Procedures**

### **6.2.1 Specimen Preparation**

Specimens for analysis will be collected as described in Table 2 at the time points indicated in Table 1. Venipuncture will be performed by trained certified nursing assistants, nurses, nurse practitioners, or physicians and collection and handling will be per the manufacturer's recommendations. A central venous catheter may be utilized for all blood sampling if the patient currently has one. Serum, plasma, and urine will be collected and stored at -80°F.

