### 6.3.2 Laboratory Evaluations

Blood and urine will be collected at the time points described in Table 1.

CBCD, LFT, ESR, 25OHD, Calcium, iPTH, UA, urine ca:cr will be performed in real time by the Fairview Diagnostics Laboratory at UMN and at Quest for subjects seen at Harbor-UCLA at baseline, 3, 6, and 12 months. BMP, LFT, and UA will be performed at UMN, Quest, or the subject's local clinical lab at weeks 4 and 6, and month 9. Anti-drug antibody testing will be performed by Intertek Pharmaceutical Services at Baseline, at weeks 3 and 6, and months 3, 6 and 12, after the first dose, and 2-3 weeks after last dose, and then every 4-6 weeks until values return to baseline. Genetic testing for mutations in TCIRG1, CLCN7, CAII, OSTM1 and RANKL genes will be performed at the Baseline visit at the University of Minnesota for patients who have not had an osteopetrosis related mutation previously identified.

25OHD will be measured by liquid chromatography tandem mass spectrometry, and an attempt will be made to maintain levels between 30 ng/ml and 75 ng/ml. Treatment of vitamin D insufficiency/deficiency will be as follows:

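### Footnote f can be read as taking the Baseline CBC and ESR from the medical record, which conflicts with Section 6.3.2 and leaves the baseline for the paired tests undefined

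*Combined protocol and SAP*

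**What the plan says.** Table 1 in Section 5.3 schedules blood count and ESR at Baseline and months 3, 6 and 12. The Baseline marks, and only those, carry footnote f: "CBC, and ESR will be obtain from the patient's medical record when available". The same footnote covers height in subjects under 18, hospitalizations and infection data. Appendix B repeats both the marks and the footnote.

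Section 6.3.2 gives a different source for the same cell: "CBCD, LFT, ESR, 25OHD, Calcium, iPTH, UA, urine ca:cr will be performed in real time by the Fairview Diagnostics Laboratory at UMN". The other site uses a second laboratory, and the visits, baseline among them, are listed there too: "at Quest for subjects seen at Harbor-UCLA at baseline, 3, 6, and 12 months". Section 6.2.1 agrees with it: "Specimens for analysis will be collected as described in Table 2 at the time points indicated in Table 1". Table 2 sends both tests to Quest or Fairview, not batched.

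Section 4.2 uses these measurements twice. Hypothesis 1 begins "Compared to baseline, treatment with IFN" and includes white cells and platelets (1e) and ESR (1g). Hypothesis 2 begins "Compared to the 12 months prior to study entry (based on medical record review or subject recollection), treatment with IFN" and includes the same measurements (2c, 2d). Section 7.2.2 gives one method for both, paired t-tests or chi-squared tests of change from baseline to 12 months, at p < 0.05.

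**The concern.** Two operative parts of the protocol name different sources for one Baseline cell, and no rule says which governs. A coordinator working from the schedule could enter a chart value wherever one exists and a study-laboratory value otherwise. The paired analysis would then mix sources within one column of baselines.

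This matters more than usual here because the trial has a single arm, so no control group absorbs an artefact in the baseline. Under Section 5.4.5 a low hemoglobin, neutrophil or platelet value can be the reason a subject is eligible. Section 5.4.3 confirms eligibility from medical records, and Table 1 schedules no blood count at Screening. A chart count may therefore be the very value that qualified the subject, and such values tend to move back toward the usual level without any drug effect. Chart values may also come from other laboratories and other dates. Footnote d delays bone-marker sampling until more than 2 weeks after a fever or fracture; nothing comparable protects a chart blood count or ESR.

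**Working it through.** The point is textual. The plan gives no power, effect size or SD for these endpoints, and the sample size of 10 rests on feasibility (Section 7.2.1), so there is no plan figure to reproduce.

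**The texts side by side**

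1. *Source of the Baseline value.* Footnote f: the medical record, if it has one. Sections 6.3.2 and 6.2.1 with Table 2: Fairview or Quest, on a specimen taken at Baseline. These conflict on their face.
2. *Does the footnote add or substitute?* It does not say. On the infection rows the record, or failing that the subject's memory, supplies the Baseline entry itself. For height, Section 6.3.1 collects record values from 6 and/or 12 months earlier, and Section 6.3.3 separately requires three stadiometer readings, so the record value is an addition. The footnote's own items point both ways.
3. *Date.* The footnote has no window. Hypothesis 2 is limited to the 12 months before entry. Section 6.3.1 dates height but not blood count or ESR.
4. *Which value is tested?* Section 7.2.2 does not separate the hypothesis 1 comparison from the hypothesis 2 comparison.

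**What would follow if chart values served as baseline** (illustration only; correlations and shifts are assumptions, and a two-sided test is assumed because the plan does not state sidedness)

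*Regression to the mean.* With equal means and SDs at both times and correlation ρ, a value selected for being low is expected to recover a fraction 1 − ρ of its distance below the mean. For ρ = 0.8 this is 1 − 0.8 = 0.2; for ρ = 0.5 it is 1 − 0.5 = 0.5.

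*False positives from a pure shift.* A paired t-test with n = 10 rejects when |t| > 2.262 (9 df). A shift of δ SDs of the differences gives a noncentral t with noncentrality δ√10:

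| δ | δ√10 | P(p < 0.05), no drug effect |
|---|---|---|
| 0.25 | 0.79 | 11% |
| 0.50 | 1.58 | 29% |
| 0.75 | 2.37 | 56% |

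*Loss of precision.* The SD of differences is SD × √(2(1 − ρ)). At ρ = 0.8 this is 0.632 SD. With n = 10, 80% power needs 0.996 SDs of the differences, that is 0.996 × 0.632 = 0.630 SD. For that same effect, if chart values lowered ρ:

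| ρ | SD of differences | Standardized effect | Power |
|---|---|---|---|
| 0.8 | 0.632 | 0.996 | 80% |
| 0.7 | 0.775 | 0.813 | 63% |
| 0.6 | 0.894 | 0.704 | 51% |
| 0.5 | 1.000 | 0.630 | 43% |

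Hypotheses 1e and 2c are limited to subjects with low counts at baseline, so the count analyses may have fewer than 10 pairs. At n = 8 the change detectable with 80% power is already 1.16 SDs of the differences, and at n = 5 it is 1.68.

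**The case against.** The strongest reply is that the body text already settles the matter. Section 6.3.2 specifies a study-laboratory test at baseline. The footnote's list closely follows hypothesis 2, and the footnote is the only procedural text that collects chart blood counts and ESR for that hypothesis. Where the authors intend substitution they say so: footnote a lets screening evaluations count as baseline, and footnote b skips genotyping already done clinically. Placement of the mark is also weak evidence of intent, since Appendix B puts it on the RNA and DNA row as well, which the footnote does not mention.

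Most of this stands. A reader might infer that the footnote replaces the Baseline draw, or that the chart values have no time limit at all. The documents do not support either: a draw is specified, and hypothesis 2 carries a 12-month limit.

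A reader might also infer that chart values are mostly taken during illness, so that later improvement is exaggerated by a calculable amount. Nothing in the protocol says when chart values are taken. Its own example of an infection, pharyngitis in Section 8.2, includes a high neutrophil count. A chart white count raised in that way would hide the hypothesized rise, not inflate it.

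What the reply does not remove is that the likely intent is unwritten. The instruction on the schedule differs from Section 6.3.2, and Section 7.2.2 does not break the tie.

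**Conclusion.** The concern holds as a conflict over the source of a secondary-endpoint baseline. It is not a finding that the trial will use chart baselines. Footnote f can be read as setting the Baseline blood count and ESR from the record, with no window or laboratory requirement of its own, against Section 6.3.2. If it were followed literally, regression to the mean and laboratory and timing differences could distort the paired changes in white cells, platelets and ESR. Regression to the mean would push low qualifying counts upward; the net direction of the other influences is not known. The documents fix no size. The figures in the working are conditional on assumed shifts and correlations, and on chart values actually being used.

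Priority is minor to moderate. These are secondary endpoints in a 10-subject pilot whose primary endpoint is descriptive.

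**What to change.** Reword footnote f identically in Table 1 and Appendix B, and add one matching sentence to Section 7.2.2:

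- The Baseline blood count and ESR are the study-laboratory results on the sample drawn before the first dose. They are the baseline for hypothesis 1 and for the paired tests.
- Chart values of blood count, ESR and height are recorded with their dates, in addition to the Baseline measurement. They come from the 12 months before entry and serve as the historical comparator for hypothesis 2.
- Use of medical records to confirm eligibility is unchanged.

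The cost is wording only, since Section 6.3.2 already plans the draw. Two limits remain and should be acknowledged when results are reported. Hypotheses 2c and 2d still compare chart values with study-laboratory values. Hypothesis 1e still selects subjects for low counts at baseline, so some regression to the mean can persist even with a study-laboratory baseline.

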## 5.4 Study Population

This study will include patients diagnosed with osteopetrosis who are  $\geq 1$  year of age, have anemia, neutropenia, frequent serious infections, or impaired bone healing.

### 5.4.1 Sample Size

This is a pilot study; therefore, the sample size was determined based on clinician expert opinion and prevalence of the disease (estimated at 1/100,000-500,000) to estimate the number of potential participants who could be enrolled over 18 months.

### 5.4.2 Subject Recruitment

Subjects will be recruited from the Osteopetrosis Society website, clinicaltrials.gov, and provider referral.

### 5.4.3 Subject Screening

Due to the rarity of this disease patients will be traveling from all parts of the country to participate and therefore the screening may occur prior to the subject traveling to the study center to avoid unnecessary travel and therefore consent will be obtained verbally by phone when necessary (by the PI or study coordinator). At the Baseline visit, if not signed previously, consent and assent forms will be again reviewed in detail and the patient and/or their parents/legal guardians will have the opportunity to ask any questions they may have. They will also be asked to describe the protocol prior to signing these forms to ensure that all details are clearly understood. Medical records will then be reviewed to confirm eligibility.

### 5.4.4 Prior and Concomitant Therapy

Potential participants will not be enrolled if they expect to be treated with HCT within 12 months of entering the study. All other therapies are permitted.

### 5.4.5 Inclusion Criteria

Patients will be eligible to participate in the study if all of the following conditions exist:

1. Diagnosis of osteopetrosis based on radiographic findings and
2. Anemia (Hemoglobin  $<12$  g/dL) not related to iron deficiency, or
3. Neutropenia (Neutrophil count  $<1000$  neutrophils/ $\mu$ l unsupported with cytokines), or
4. Thrombocytopenia (Platelet count  $<50,000$  cells  $\times 10^9$ /L), or
5. History of impaired bone healing, or
6.  $\geq 1$  serious infection over prior year defined as requiring hospitalization and/or IV antibiotics, and
7. Age  $> 1$  year; and
8. Ability to travel to a study center for every 3-6 month study visits; and

9. Patient or parent/legal guardian is able and willing to provide informed consent. For patients 7 to 17 years of age, assent must also be provided.

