## Study Summary

Title	Open-label Phase 1/2 Study with a Single Arm of Interferon Gamma-1b Treatment of Osteopetrosis
Study Sponsor	[name], MS Assistant Professor, Pediatric Endocrinology David Geffen School of Medicine Los Angeles Biomedical Research Institute at Harbor-UCLA Medical Center
Principal Investigator (PI)	[name], MS Assistant Professor, Pediatric Endocrinology David Geffen School of Medicine Los Angeles Biomedical Research Institute at Harbor-UCLA Medical Center
Study Design	multi-center open-label phase 1/2 clinical trial
Study Duration	Subjects will participate in the study for 1 year. It is expected that enrollment will be completed in 18 months and the last subject will complete the protocol 2.5 years after study initiation.
Study Center(s)	
 
1. LABioMed at Harbor-UCLA [name] [name]
 
2. University of Minnesota [name] [name]
 

Study Objectives	
 
1. To determine the feasibility and tolerability of interferon gamma-1b treatment in patients with intermediate osteopetrosis.
 
2. To determine the safety and efficacy of interferon gamma-1b in patients with intermediate osteopetrosis.
 

Study Endpoints	
Primary Endpoint: The primary objective of this pilot study is to determine the feasibility and tolerability of interferon gamma-1b treatment for 1 year in patients with intermediate osteopetrosis. Specifically, i) the ability to enroll patients, and ii) continued treatment throughout the 1-year observational period.
 
Secondary Endpoints: The secondary objectives of this study will focus on change in immunologic and hematologic function, bone mineral density and osteoclast function, physical function and quality of life.

Number of Subjects	10
Main Inclusion Criteria	
 
• Intermediate Osteopetrosis, defined as: 
 
○ Anemia, or
 
○ Neutropenia, or
 
○ <math>\geq 1</math> serious infection over prior year defined as requiring hospitalization and/or IV antibiotics, or
 
○ History of impaired bone healing
 
 
 
• Age <math>> 1</math> year
 

Duration of Observation	1 year

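### The platelet inclusion threshold is printed in a unit that makes it 1,000 times 50,000 per microlitre, and no other section states a platelet cut-off

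*Combined protocol and SAP*

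**What the plan says.** Section 5.4.5 requires a radiographic diagnosis of osteopetrosis plus at least one of five alternatives (items 2 to 6): anemia, neutropenia, thrombocytopenia, impaired bone healing or serious infection. Item 4 reads "Thrombocytopenia (Platelet count $<50,000$ cells $\times 10^9$ /L". Item 3, directly above it, uses a different unit: "Neutrophil count $<1000$ neutrophils/ $\mu$ l unsupported with cytokines".

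Elsewhere, platelets appear without a number:

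- Section 4.2, hypothesis 2c refers to "platelet counts in patients who have lower than expected blood counts at baseline", and hypothesis 1e is equally unquantified.
- Section 8.4.3 and the monitoring plan in Appendix A name thrombocytopenia as a disease-related event and give no limit.
- Table 1 and Appendix B list "CBC with differential and platelets" at Baseline, not at Screening, with no threshold.

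The Study Summary ("Intermediate Osteopetrosis, defined as") and the opening sentence of Section 5.4 list the qualifying conditions without thrombocytopenia. The version history, through version 1.8, records no change to item 4.

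**The concern.** Item 4 puts a number that suits a per-microlitre count next to a multiplier that suits a per-litre count. Together they describe a limit that every realistic platelet count satisfies. Because items 2 to 6 are joined by 'or', a criterion met by everyone would satisfy the severity requirement for everyone, and the other four alternatives would no longer restrict entry.

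The count has to be compared with this line in practice. Section 5.4.3 describes patients travelling from across the country and says: "Medical records will then be reviewed to confirm eligibility". A blood count is also run at Baseline, where Section 6.3.2 says: "CBCD, LFT, ESR, 25OHD, Calcium, iPTH, UA, urine ca:cr will be performed in real time by the Fairview Diagnostics Laboratory"; Quest does this for subjects seen at Harbor-UCLA. Whichever source is used, the reported value needs a cut-off in a single unit. With 10 planned subjects, each eligibility decision concerns one tenth of the sample, so the criterion should be auditable as written.

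**Working it through.** **Inputs.** The platelet limit as printed in Section 5.4.5, item 4: 50,000 cells x 10^9/L. The neutrophil limit in item 3: 1,000 per microlitre. Conversion: 1 L = 10^6 microlitres.

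**Step 1: the printed limit per litre.** 50,000 x 10^9 = 5 x 10^13 per litre.

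**Step 2: the printed limit per microlitre.** 5 x 10^13 / 10^6 = 5 x 10^7 = 50,000,000 per microlitre.

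**Step 3: comparison with the same number read per microlitre.** 50,000 per microlitre x 10^6 = 5 x 10^10 per litre = 50 x 10^9/L. The ratio is 5 x 10^13 / 5 x 10^10 = 1,000. Put the other way, 50,000 per microlitre is 50 / 50,000 = 0.1% of the printed limit.

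**Step 4: the neighbouring item.** 1,000 neutrophils per microlitre = 10^9 per litre = 1 x 10^9/L, so item 3 is coherent in its own unit. The fault is confined to item 4.

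**Step 5: what the simplest repairs would give.**

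| Repair | Result | Per microlitre |
|---|---|---|
| Keep 50,000, use item 3's unit | 50,000 per microlitre | 50,000 |
| Keep 10^9/L, drop the thousands | 50 x 10^9/L | 50,000 |
| Keep 50,000, change the exponent | 50,000 x 10^6/L | 50,000 |

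All three agree. They are unit equivalences and do not show what the sponsor intended.

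**Step 6: search for a confirming figure.** The Study Summary and Sections 4.2, 5.3 (Table 1), 5.4, 6.2.1 (Table 2) and 8.4.3, with Appendices A and B, were read for a second platelet cut-off. None gives one.

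**The case against.** The strongest reply is that nobody would be misled. The item is labelled as thrombocytopenia, a limit met by every count contradicts that label, and the three obvious repairs lead to the same value. On this view the slip is typographical and confirmation by the sponsor is a formality. Much of this stands: the literal reading is implausible and the practical effect is probably small. It does not make the line correct. Site staff should not have to correct an eligibility threshold silently, and no other section backs the correction.

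A second reply is that the error rests on one exponent in text extracted from a PDF; 10^6 in place of 10^9 would make the line coherent. There is no sign of a misread, but a glance at the source page would settle it.

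A third is that Table 1, footnote f ("CBC, and ESR will be obtain from the patient's medical record when available") looks more like collection of historical data for the 12-month comparison in Section 4.2 than a source for eligibility. That is a fair reading, and the footnote does not mention eligibility. The point does not need it, because Section 5.4.3 says directly that records are used to confirm eligibility.

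Finally, the omission of thrombocytopenia from the Study Summary and Section 5.4 is a separate and weaker matter. One is headed as main criteria and the other is a one-sentence overview, while Section 5.4.5 is the operative list. It is worth tidying but adds no weight to the unit error.

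**Conclusion.** The concern holds. The only platelet cut-off in the available text is wrong as printed by a factor of 1,000, and it sits in the operative eligibility list. It affects one of five alternative routes to entry. The arithmetic needs no assumption beyond the printed text being a faithful copy of the source page.

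The consequences are limited. No mis-enrolment is shown, the documents do not allow an enrolment effect to be estimated, and the sample size of 10 rests on feasibility (Sections 5.4.1 and 7.2.1), so no design or analysis figure changes. The line should be corrected because it decides eligibility and cannot be applied as written.

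**What to change.** The sponsor should confirm the intended platelet threshold and restate Section 5.4.5, item 4 in one coherent unit. If 50,000 per microlitre is what was meant, the equivalent is <50 x 10^9/L; the choice of threshold is the sponsor's.

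As a secondary edit, reconcile the Study Summary and the opening sentence of Section 5.4 with Section 5.4.5 on whether thrombocytopenia is a qualifying condition.

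The cost is a one-line correction and up to two wording edits in a single amendment, with the IRB approval that Section 6.7 requires. No sample size or analysis text changes.

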## 6.3 Clinical Procedures

### 6.3.1 Medical History

A study physician and/or study coordinator will review the following with the subject/parent or legal guardian at the screening baseline visit:

- Current and past 1 year prescription medications and doses,
- current and past medical history,
- review of systems,
- family history,
- number of hospitalizations over the last 12 months, and

- number of days treated with antibiotics over the last 12 months.

For patients <18 years of age, height data will be collected from 6 and/or 12 months prior to the baseline visit.

Changes in the medical history and a complete review of systems will be reviewed at each subsequent visit.

If a subject is unable to return to the clinical site for the Month 3 visit they will be contacted via telephone to discuss any changes in health since their last study visit and then withdrawn from the study. Three attempts will be made to contact the subject by phone before terminating the patient on the study.

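### The year that can qualify a subject through a serious infection is also the reference year for hypotheses 2a and 2b, so a fall is expected under a null drug to the extent that subjects enter only by that route

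*Combined protocol and SAP*

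**What the plan says.** Section 5.4.5 requires radiographic osteopetrosis plus any one of five alternatives: anemia, neutropenia, thrombocytopenia, impaired bone healing ("History of impaired bone healing, or") or at least one "serious infection over prior year defined as requiring hospitalization and/or IV antibiotics".

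Section 4.2 sets the reference for its second group of hypotheses: "Compared to the 12 months prior to study entry (based on medical record review or subject recollection". Hypothesis 2a is "Decreased number of hospitalizations for infection" and 2b is "Decreased number of days treated with antibiotics". Section 6.3.1 collects the history to match, including the "number of hospitalizations over the last 12 months". A footnote to Table 1 in section 5.3 says "Screening visit will be within 3 months of baseline visit", so the eligibility year and the reference year can be offset by up to 3 months.

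The trial has one arm and plans 10 subjects. Sections 7.1 and 7.2 contain no control, no other look-back period, no split by entry route and no caveat on this selection. Section 7.2.2 assigns paired t-tests or chi-squared tests to hematologic function, immune function and bone mineral density. It does not name infection hospitalizations or antibiotic days.

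**The concern.** The event that can qualify a subject is the event that 2a and 2b count, in nearly the same window. A subject who enters only because of an infection last year has a reference year chosen for being bad, while the treated year is not chosen at all. The average therefore drifts down without any treatment effect (regression to the mean), and a single arm offers nothing to subtract it from.

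At stake is the reading of a clinically prominent outcome. Section 2.2 cites fewer severe infections as earlier evidence for this drug, and section 2.3 plans to use encouraging efficacy data to raise awareness among clinicians. The bias lies in the means, so it is present whether the result is tested or only described.

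**Working it through.** **Plan's own figure.** There is none to reproduce. The sample size of 10 rests on feasibility, with no infection rate, effect size or power.

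**Assumptions.** These are not from the documents.
- Serious infections are event counts with mean L per year. The main range is L = 0.5 to 1.0, and L = 2 is also shown.
- Each subject has the same underlying rate in both years, so the drug is null.
- The eligibility and reference years coincide, and every qualifying event counts in the outcome.
- A candidate qualifies by another criterion with probability q, independently of infection; otherwise at least one prior-year infection is needed.
- The test is a two-sided paired t-test at 0.05 with n = 10, counted when significant and in the direction of a decrease (nominal 2.5%).

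**Expected fall when all subjects are selected on infection (q = 0).**

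Poisson counts: the prior-year mean is L/(1 − e^(−L)), the treated-year mean is L, and the fall is e^(−L).
- L = 0.5: 0.5/0.393 = 1.27 to 0.50, a fall of 61%.
- L = 1.0: 1/0.632 = 1.58 to 1.00, a fall of 37%.

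Rates varying between patients (gamma, shape 1): the prior-year mean is 1 + L, the treated-year mean is (1 + L) − 1/(1 + L), and the fall is 1/(1 + L)².
- L = 0.5: 1.50 to 0.83, a fall of 44%.
- L = 1.0: 2.00 to 1.50, a fall of 25%.

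**Expected fall for general q.** Poisson: (1 − q)e^(−L). With q = 0.5 this is 30% at L = 0.5 and 18% at L = 1.0; under gamma shape 1 it is 22% and 12%. With q = 1 it is 0.

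**Simulated rate of a false significant decrease, n = 10.**

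| Scenario | Poisson, L = 0.5 / 1.0 / 2.0 | Gamma shape 1, L = 0.5 / 1.0 / 2.0 |
|---|---|---|
| All 10 selected (q = 0) | 67% / 26% / 7% | 41% / 18% / 8% |
| Half of candidates qualify anyway (q = 0.5) | 9% / 7% / 4% | 6% / 5% / 4% |
| q = 0.8 | 3% / 3% / 3% | 2% / 3% / 3% |
| Nobody depends on item 6 (q = 1) | 2% / 2% / 2% | 1% / 2% / 2% |

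The q = 0.5 row is not the same as half of those enrolled. Under Poisson, the enrolled share that depends on item 6 is 0.5(1 − e^(−L))/[0.5 + 0.5(1 − e^(−L))], which is 28% at L = 0.5 and 39% at L = 1.0. If exactly 5 of 10 enrolled were selected on infection, the false-decrease rate at these two rates would be 7 to 18%.

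**Two candidate remedies under the same null model.**
- *Reference of months 13 to 24, all subjects.* That year was not used for selection, so its mean equals the treated-year mean (for example 0.50 and 0.50 at L = 0.5, Poisson, q = 0). The false-decrease rate is about 2% in every scenario in the table.
- *Restricting to subjects who did not meet item 6.* They had no qualifying infection, so their prior-year count is 0. The treated-year mean is 0.50 or 1.00 (Poisson, L = 0.5 or 1.0), or L/(1 + L) = 0.33 or 0.50 (gamma shape 1). Only a rise is possible, which is the opposite bias.

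**The case against.** Infection is one of five routes, and the bias comes only from subjects who would not have qualified otherwise. A reader might infer from the entry rule that a fall is certain, or that the 18 to 67% range describes this trial. The documents support neither. The upper figures need all 10 subjects to be selected on infection at 0.5 to 1.0 events per year. Section 5.4 speaks of frequent serious infections, and at 2 per year the rate is about 7 to 8% even with all 10 selected.

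A reader might also infer that anyone entering through item 6 must have a non-zero hospitalization count in the reference year. That is not so. The criterion can be met by IV antibiotics without admission, in which case 2b is affected and 2a is not. The screening window can also shift the two years apart by up to 3 months, leaving an overlap of about 9 to 12 months.

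The paired t-test is this review's assumption, since section 7.2.2 does not name these outcomes. The calculation models events, so it gives no figure for antibiotic days.

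Finally, this is a feasibility pilot. The primary endpoint is untouched, and section 2.3 does not mention infection specifically.

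All of this limits the size and weight of the point. It does not remove the direction of the bias, and the plan does not call for the qualifying route to be reported, so a reader of the results could not judge how much applies.

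**Conclusion.** The concern holds in conditional form. Because item 6 and hypotheses 2a and 2b share essentially one window in a single arm, a fall in infection hospitalizations, antibiotic days or both is expected under a null drug to the extent that subjects enter only through item 6. Under the stated assumptions the null fall ranges from 25 to 61% with all 10 selected, down to nothing if no one depends on that route. The documents do not allow a narrower statement. As planned, a fall in 2a or 2b could not be attributed to the drug. The feasibility and tolerability conclusions are unaffected.

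One separate matter acts in the same direction and is not in these figures. The on-treatment item is "Number of hospitalizations in prior 3 months", asked at months 3, 6 and 12 but not month 9, so it covers 9 of 12 months. If adverse-event records and history updates do not fill months 6 to 9, that alone gives about a 25% apparent fall (1 − 9/12), whichever reference year is used.

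**What to change.** In sections 4.2, 6.3.1 and 7.2.2:

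1. Extend the existing record review to months 13 to 24 before entry, and use that period as the reference for 2a and 2b in all subjects with records. Limiting it to those who met item 6 would leave the others on a prior year with no infection hospitalizations by rule, and pooling would carry that reverse bias. Count the months back from the date on which eligibility was assessed. If screening is 3 months before baseline, the eligibility year reaches 15 months before baseline and would overlap a period counted from there.
2. Report the prior-12-month comparison as descriptive only, stating that a fall is expected from the entry rule and cannot be attributed to the drug.
3. Record on the CRF every criterion each subject met. If results are split, split by whether the subject qualifies under items 2 to 5 regardless of infection history, or only through item 6. Draw no efficacy inference from the subjects who did not meet item 6.

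The cost is one CRF field, some wording and a longer record request, with no new visits. The drawbacks are incomplete older records, no full months 13 to 24 for children under 2, and probably a smaller apparent infection benefit.
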